Importantly, residual leukemia was morphologically detectable in 38/48 patients on day 8 prior to bevacizumab. On Day 15 (one week following bevacizumab), 28/48 patients had cleared morphologic leukemia. 16 patients achieved complete remission, including 2/3 newly diagnosed poor-risk AML, 9/18 patients in first remission, and 5/27 patients with primary refractory disease. 7 patients achieved PR, for an overall response rate of 48% following one cycle of treatment. VEGF receptor FLT-1 on bone marrow cells was greater than in normal bone marrow in 12/13 patients examined. On day 8, blasts continued to express FLT-1 in 8/10 patients. Serum free-VEGF was detectable in 14/21 patients prior to treatment (median concentration 12 pg/mL). Day 8 concentrations were higher than on day 0 in 11 patients including 4 patients in whom VEGF had been undetectable, while VEGF concentration had decreased in 6.

Among 15 patients in whom serum was sampled two hours following bevacizumab infusion, 10 had complete suppression of detectable VEGF, while 4 patients had VEGF concentrations ranging from 24 – 82% of the pre-bevacizumab baseline. Sequential examination of bone marrow microvessel density revealed significant decreases in 8/11 patients.

This study confirmed the widespread expression of VEGF in patients with relapsed and refractory AML, and suggested that effective VEGF inhibition could substitute for a toxic second administration of chemotherapy drugs in a timed sequential chemotherapy model, leading to a very promising response rate. This combination was not further developed due to lack of priority from the manufacturer of bevacizumab, despite great interest from the Johns Hopkins group and the Cancer Therapy Evaluation Program. (Personal communication).

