1.3 Objectives

1.3.1 *Primary objective*

Phase I: To determine the safety and tolerability of Nintedanib in combination with intensive AML chemotherapy; Idarubicin and cytarabine after 1 cycle of treatment

Randomized Phase II: To determine the complete remission rate (CR+ CRp) of chemotherapy ; Idarubicin and cytarabine + nintedanib compared to chemotherapy Idarubicin and cytarabine +placebo after 1 cycle of treatment

1.3.2 *Secondary Objectives*

To determine overall response rate of nintedanib+ chemotherapy as compared to placebo + chemotherapy

To determine the overall survival and leukemia free survival of patients treated with nintedanib+chemotherapy as compared to placebo+chemotherapy.

To determine the percentage of patients bridging to allogeneic transplantation as well as time to transplantation after nintedanib+chemotherapy as compared to placebo+chemotherapy

To determine hematological response rate of the nintedanib+ chemotherapy as compared to placebo + chemotherapy

Phase II: To determine the safety and tolerability of nintedanib+chemotherapy as compared to placebo+chemotherapy

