1.4.2 Secondary endpoints

Overall response rate will be defined according to IWG 2003 criteria⁴⁶ and includes: CR, CRp, CRI, PR, and marrow leukemia free state (MLFS). Rates of hematological improvements (as defined by IWG 2006 Myelodysplastic syndromes criteria⁴⁷) will also be recorded.

Overall Survival will be defined from time of treatment initiation to the time of last follow-up or death. Survival with censoring patients at the time of transplantation will also be evaluated.

Leukemia free survival will be defined from time of documentation of complete remission (CR+CRp+CRI) to the time of last follow-up, relapse, or death of any cause. Survival with censoring patients at the time of transplantation will also be evaluated.

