Phase II: Based on the phase I dose, in the randomized phase II, the combination of chemotherapy + Nintedanib will be compared with chemotherapy+placebo. The AML chemotherapy induction and consolidation regimen occur at an inpatient hospital stay typically averaging 5 weeks and is Standard of Care (SOC) per local hospital policy. The induction and consolidation chemotherapy regimen for Phase II are identical to that in Phase I and combines Idarubicin 12mg/m²/d IV push over 10-15 minutes days 1 to 3 and Cytarabine 0.667g/m²/d (24 hr. IV infusion) day 1 to 3. In Phase II, patients will be randomized to receive the combination chemotherapy in addition to Nintedanib (dose determined in Phase I) at Day 8 through day 28 (end of cycle) or placebo at Day 8 until day 28 (end of cycle). Patients may be discharged based on local SOC and re-admitted prior to the start of the next cycle however, some patients will stay in the hospital continuously (especially between the first two induction cycles). Induction cycle 2 can begin as early as study day 29 regardless of count recovery status if the investigator believes it would be clinically beneficial. Patients can be given a “break” between cycles of induction based on investigator’s clinical judgement and clinical response. Count recovery is necessary before a consolidation cycle can begin. If count recovery is not achieved 60 days after Cycle 1 Day 1, the patient is removed from the study. **Figure 2.** describes the overall

strategy of the Phase II portion of the study. All patients will be evaluated for response based upon count recovery or following day 45, whichever comes first. Patients without count recovery and without signs of bone marrow leukemia at day 45 will be followed up to day 60. If no recovery is observed at day 60, patients will be removed from protocol and considered a failure.

In phase I, patients who fail to achieve CR or CRp based on IWG 2003 AML response criteria (pg. 77) after first cycle of treatment may receive a second cycle of treatment using Nintedanib+ chemotherapy. Patients who achieve CR or CRp after one or two induction cycles may receive up to 2 cycles of consolidation using the same regimen.

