1.10.2 Evaluation during treatment period

The treatment period begins Cycle 1 Day 1 and can continue until up to 30 days after the last dose of Nintedanib. The treatment period can include a maximum of 2 (28 day) induction and 2 (28 day) consolidation cycles. If Maintenance therapy is indicated, patients will be followed monthly for the first 12 months and then every three months for the following year (a maximum of 24 months). Number and type of cycle will vary by patient and according to local SOC procedures.

Labs between day 8 and counts recovery can be done +/-2day

The following assessments need to be completed:

- Physical examination daily from day 1 to day 6 and then twice weekly during the induction cycle(s) 1 and 2 (if receiving a second cycle). During consolidation cycle(s) 1 and 2 at day 1, then weekly, and at the end of each cycle.
- ECOG performance status weekly during the first induction cycle and at the end of each cycle thereafter,
- Any adverse event,
- Concomitant medication,
- CBC with differential daily from day 1 to day 5 and then every other day for the first cycle and three times weekly of each cycle thereafter, (differential done as per hospital standard of care) entire panel required at response evaluation
- Serum chemistry daily from day 1-5. Then at a minimum of twice weekly, 3-4 days apart (+/- 2 days) during the first cycle and every other week each cycle thereafter. It includes AST, ALT, alkaline phosphatase, total bilirubin, BUN, serum creatinine, glucose, calcium, sodium, potassium, chloride, bicarbonate, total protein, albumin, LDH and magnesium
- Pregnancy test prior the beginning of each new treatment cycle (women of childbearing potential only)
- Coagulation profile daily from Day 1-5 of cycle 1 and then weekly during the first two cycles: prothrombin time, activated partial-thromboplastin time, fibrinogen,
- Bone marrow evaluation will be performed in patients with complete clearance of blasts in the blood on Day 14 (+/- 1 day) and at the end of cycle 1 Day 28 (+/- 7 days) and decided by local investigator based on count recovery. Threshold: ANC at 1 and PLT at 50,
- Assess LVEF before cycle 2; this can be done any time after Cycle 1 day 14 up to the start of cycle 2, ideally closer to cycle 2 Day 1 using 3D Echocardiogram or the biplane Simpson method.

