1.13 Correlative studies

Sampling flow chart

Peripheral Blood (PB)=20 ml EDTA, bone Marrow Aspirate (BMA)= 8 ml baseline, 5-6 ml follow-up, Bone marrow biopsy (BMB), * potential significant hypoplasia

- Baseline (day -14 to – 5): PB, BMA, BMB
- Day 8 (day 5 post chemo, day 0 of Nintedanib) = PB*
- Day 8 OPTIONAL CONSENT (day 5 post chemo, day 0 of Nintedanib) = BMA
- Day 14 (day 11 post chemo, day 6 of Nintedanib) = PB*, BMA*, BMB*
- Day 28 (day 25 post chemo, day 20 of Nintedanib) = PB, BMA, BMB
- End of Treatment= PB, BMA, BMB

Correlative studies

1/ Genomic profiling (baseline)

There is a significant diversity in molecular profiling of relapse/refractory AML and specific aberrations may be associated with differential response to chemo/nintedanib. Moreover, it is anticipated that several of the pathways that will be evaluated by CyToF may already been triggered by activating mutations at baseline (e.g. FLT3 ITD and STAT).

Objective: Determine the mutational landscape of the population. Correlate with response and pathway activation

Methods: Whole exome sequencing/ Ion Torrent 490 gene panel / RNA sequencing

2/ Bone Marrow microvessel density (Baseline, day 14, day 28)

Microvessel density is a classical pharmacodynamic read out of VEGF inhibition. It can be evaluated on BM biopsies routinely

Objective: determine the density of microvessel on bone marrow biopsies and correlate it with Nintedanib exposure and response

Methods: Immunostaining on BM trephine biopsy sample (VWF, CD31, CD34 staining)

Optional= Stem cell niche evaluation

3/ VEGF expression levels (Baseline, day 8, 14, and 28)

VEGF can be secreted by bone marrow stroma and has been also described as potentially secreted by some AML blasts. Bone Marrow stress induced by chemotherapy can also trigger a VEGF response that may subsequently affect survival of AML blast and normal cells recovery pattern. VEGF inhibition by bevacizumab has been described as associated with an increase in VEGF levels.

Objective: Determine patterns of VEGF expression before and during treatment. Evaluate the effect of Nintedanib on these patterns. Correlate it with Response

Methods: Quantitative assessment by ELISA (Quantikine R&D).

Optional: Aliquoted frozen serum will be stored and can be used to evaluate other cytokines related to Nintedanib (FGF, PDGF).

4/ Nintedanib target receptors and downstream pathways analysis (Baseline, day 8, 14, and 28)

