1.25.3 IWG response criteria

Primary endpoint will be based on IWG 2003 AML response criteria⁴⁶

- **Morphologic complete remission (CR):** ANC \geq 1,000/mcl, platelet count \geq 100,000/mcl, < 5% bone marrow blasts, no Auer rods, no evidence of extramedullary disease. (No requirements for marrow cellularity, hemoglobin concentration).
- **Morphologic complete remission with incomplete blood count recovery (CRi):** Same as CR but ANC may be < 1,000/mcl but >500 mcl and/or platelet count < 100,000/mcl but >20,000/mcl
- **Partial remission (PR):** ANC \geq 1,000/mcl, platelet count $>$ 100,000/mcl, and at least a 50% decrease in the percentage of marrow aspirate blasts to 5-25%, or marrow blasts < 5% with persistent Auer rods.
- **Marrow Leukemia Free State:** < 5% bone marrow blasts, no Auer rods, no extra medullary disease. No requirement on cytopenias

Secondary Endpoint will also include evaluation of hematological improvement based on IWG MDS 2006 criteria⁴⁷

- **Erythroid response (pretreatment <11 g/dL):** Hgb increase at least by 1.5 g/dL. Relevant reduction of units of RBC transfusions by an absolute number of at least 4 RBC transfusions/8 wk compared with the pretreatment transfusion number in the previous 8 wk. Only RBC transfusions given for a Hgb of below or equal to 9.0 g/dL pretreatment will count in the RBC transfusion response evaluation
- **Platelet response (pretreatment 100x10⁹/L):** Absolute increase of at least 30x10⁹/L for patients starting with more than 20x10⁹/L platelets. Increase from less than 20x10⁹/L to more than 20x10⁹/L and by at least 100%
- **Neutrophil response (pretreatment, <1.0x10⁹/L)** At least 100% increase and an absolute increase of at least 0.5x10⁹/L

**1.25.4 Common toxicity criteria for adverse events
(CTCAE)**

Please refer to CTCAE v4.03, a new version of the CTEP, NCI CTC v4.0, includes Adverse Events applicable to all oncology clinical trials regardless of chronicity or modality:

1.25.5 Procedures for the follow-up of a potential DILI case in IIS with nintedanib

Introduction

Drug-induced liver injury

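### Overall response counts marrow leukemia-free state under a rule with no blood-count floor, no specimen-adequacy requirement and no link to the protocol's own response evaluation

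*Combined protocol and SAP*

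**What the plan says.** Section 1.3.2 makes overall response a between-arm secondary objective: "To determine overall response rate of nintedanib+ chemotherapy as compared to placebo + chemotherapy". Section 1.4.2 says the rate "includes: CR, CRp, CRI, PR, and marrow leukemia free state (MLFS", and gives it no assessment day.

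Section 1.25.3 defines MLFS as "< 5% bone marrow blasts, no Auer rods, no extra medullary disease. No requirement on cytopenias". The other categories printed there all carry a neutrophil and platelet condition: full thresholds for CR and PR, lower floors for CRi. MLFS has none, and nothing is said about cellularity or a minimum number of cells.

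Timing appears elsewhere, in section 1.5.1: "All patients will be evaluated for response based upon count recovery or following day 45, whichever comes first". That section then deals with patients whose marrow shows no leukemia at day 45 but whose counts have not recovered. They are followed to day 60 and, if still not recovered, leave the protocol as failures. The same section lets induction cycle 2 begin from day 29 whatever the counts.

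On marrow sampling, section 1.10.2 states "Bone marrow evaluation will be performed in patients with complete clearance of blasts in the blood on Day 14 (+/- 1 day" and adds a marrow at day 28 (+/- 7 days), which the local investigator decides on from count recovery. The sampling chart in section 1.13 marks the day-14 samples for "potential significant hypoplasia".

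**The concern.** MLFS is the only route to overall response that blood counts do not guard. After idarubicin and cytarabine a marrow can hold few blasts because it holds few cells of any kind. The printed rule does not separate that state from clearance of leukemia in an assessable marrow. If emptied marrows are scored, overall response partly measures the cytotoxic effect of chemotherapy that both arms receive, and it becomes hard to read as evidence on nintedanib.

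The rules also disagree with each other. The patient whom section 1.5.1 calls a failure at day 60 is the patient whom section 1.25.3 describes as MLFS. Two analysts following the protocol could report different overall response rates from the same data.

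There is a further knock-on. In phase II, section 1.5.1 unblinds patients who fail to achieve response after cycle 1 and offers crossover to those on placebo, without saying whether MLFS counts as response. The phase I text in the same section uses CR or CRp.

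**Working it through.** **Step 1. The rules side by side.**

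| Patient after cycle 1 | Sections 1.4.2 and 1.25.3 | Section 1.5.1 |
|---|---|---|
| Under 5% blasts, no Auer rods, no extramedullary disease, counts not recovered at day 60 | MLFS, so overall responder | Failure |
| Aplastic specimen meeting the same three conditions | MLFS, so overall responder | Adequacy not addressed |
| Cycle 2 started between day 29 and day 45, counts not recovered | No rule on which marrow governs | Neither evaluation trigger has been reached |

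The first row is a direct conflict. The second and third are gaps. In the third, cycle 2 can start up to 45 - 29 = 16 days before the day-45 trigger, so the cycle-1 classification may have to come from a day-14 or day-28 marrow taken before recovery.

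**Step 2. How far early clearance can exceed remission.** The plan gives no figure for overall response, so there is no design number to reproduce. The nearest figures are those of the bevacizumab study in section 1.2.2, with 16 CR and 7 PR: (16 + 7)/48 = 47.9%, which matches the 48% stated there. In the same study, "On Day 15 (one week following bevacizumab), 28/48 patients had cleared morphologic leukemia".

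- Cleared by day 15: 28/48 = 58.3%.
- CR: 16/48 = 33.3%.
- Cleared among those without CR, assuming all 16 CR patients had cleared: (28 - 16)/(48 - 16) = 12/32 = 37.5%. If fewer CR patients had cleared, this share would be higher.

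**Step 3. Illustration with equal shares.** Let q be the share of patients without CR who are scored MLFS. An arm with CR rate p then has rate p + (1 - p)q. With the 40% and 15% CR rates of section 1.7 and q = 0.375 in both arms:

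- Nintedanib: 0.40 + 0.60 x 0.375 = 0.625.
- Placebo: 0.15 + 0.85 x 0.375 = 0.469.
- Difference: 0.25 x (1 - 0.375) = 0.156, against 0.25 without MLFS.

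**Step 4. Unequal shares.** The difference is 0.25 + 0.60 x q(nintedanib) - 0.85 x q(placebo). It shrinks only while q(nintedanib) is below 0.85/0.60 = 1.42 times q(placebo). Two assumed cases show the spread:

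- q = 0.40 on nintedanib and 0.20 on placebo: 0.64 - 0.32 = 0.32, an inflated gap.
- q = 0.20 on nintedanib and 0.375 on placebo: 0.52 - 0.469 = 0.051, a gap almost gone.

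The direction therefore depends on quantities the documents do not give.

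**The case against.** The strongest reply is that response timing is stated. Section 1.5.1 places evaluation at count recovery or after day 45, and no section makes day 14 a response evaluation or says that the best of any marrow counts. That stands. A reader might infer that the day-14 nadir marrow scores as a response, or that patients who die in aplasia become responders. The documents do not support either as a stated rule. They only fail to exclude them, because 1.4.2 and 1.25.3 never refer to 1.5.1.

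Nor are day 14 and day 28 the only cycle-1 marrows. Section 1.10.4 and the study calendar in 1.25.7 add an end-of-treatment marrow in patients whose blood has cleared of blasts, and section 1.6 adds a discretionary marrow by day 35 in phase I. It is therefore not established that a nadir specimen will be the last on file. None of these is named as the marrow that decides response, however.

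The 37.5% is also a weak guide to this trial. It was measured a week after bevacizumab; on day 8, before that drug, 38 of 48 patients still had detectable leukemia. The documents give no clearance rate for chemotherapy alone. The 40% and 15% are CR rates, whereas overall response also includes CRi and PR.

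The day-60 failure may be meant for the primary endpoint alone, which would remove the conflict, but the text does not say so. The cited IWG 2003 source may contain an adequacy requirement; that cannot be checked here, and the printed appendix does not show one.

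Finally, the stakes are limited. Section 1.7 tests each arm against a historical rate and compares the arms only qualitatively.

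**Conclusion.** The concern holds as a gap and a conflict in the definition of a secondary endpoint. MLFS counts toward overall response with no blood-count floor, no specimen-adequacy rule and no link to the section 1.5.1 evaluation. A patient with a clear marrow and no recovery at day 60 is classified in two ways, and an early cycle 2 leaves the governing marrow undefined.

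The size is uncertain. The fall from 25 to about 16 points is an illustration. It assumes equal MLFS shares in both arms, all 16 CR patients among the 28 cleared, a clearance rate borrowed from marrows taken after bevacizumab, and CR rates as the base. It is tempting to conclude that MLFS dilutes the arm difference. That follows only if the nintedanib share stays below 1.42 times the placebo share; above that, the difference is inflated.

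The primary endpoint is unaffected, since MLFS is not part of it. The change is still worth making, because it decides who counts as a responder in a stated between-arm comparison.

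**What to change.** In sections 1.4.2 and 1.25.3:

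- Tie overall response, and MLFS within it, to the section 1.5.1 response evaluation, and say which marrow governs when cycle 2 starts before that evaluation.
- State that the day-14 marrow does not count toward overall response.
- Require a specimen adequate for a blast count; do not score aplastic or inadequate specimens as MLFS.
- Count death or leukemic regrowth before the evaluation as non-response.
- Reconcile MLFS with the day-60 failure rule, and with the undefined term for failure to respond that triggers unblinding and crossover in section 1.5.1.
- Report overall response with and without MLFS.

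The cost is a few sentences and one extra table row. The reported overall response rate will be somewhat lower, and a patient whose only marrow is an early or inadequate one will count as a non-responder.

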1.25.7 Study Calendar

Screening and Cycle 1 (Induction Therapy)

	Screening		Day																								END Of Treatment		
	-14 to - 5	-1	1	2	3	4	5	6	7	8	9	10	11	12	13	14	15	16	17	18	19	20	21	22	23	24	25	26	27
Informed Consent	x																												
Medical History	x																												
Additional exams (Lumbar puncture, CT, Pet-CT) ^b	x																												
EKG, Cardiac Echo, and CXR ^m	x																												x
Hepatitis B, C, HIV1 & HIV2 serologies	x																												
Bacterial, fungal & viral cultures throat, stool & urine ^b		x																											
Bone Marrow Evaluation & Cytogenetics	x																												
Correlative Studies (Blood)	x									x ^l							x ^l										x	x	
Correlative Studies (Bone Marrow)	x								x ^{gl}							x ^l											x	x	
Concomitant Medications ^q	x																												
Bone Marrow Biopsy ^k																x ^l												x ^p	x
Physical Exam ^{c, 0}	x	x	x ^a	x	x	x	x	x		x ^h		x ^h		x	x														
ECOG PS	x	x				x ⁱ					x ⁱ				x ⁱ			x ⁱ			x ⁱ							x	
CBC with differential ⁿ	x	x	x ^a	x	x	x	x	x	x ^j	x ^j	x ^j	x ^j	x ^j	x ^j	x ^j	x ^j	x ^j	x ^j	x ^j	x ^j	x ^j	x ^j	x ⁱ	x ⁱ	x ⁱ	x ⁱ	x		
Serum chemistry ^d	x	x	x ^a	x	x	x	x	x		x ^h	x ^h		x ^h			x ^h		x											
Pregnancy testing	x	x	x ^a																										
Coagulation Profile ^e	x	x	x ^a	x	x	x	x	x		x ⁱ				x ⁱ					x ⁱ										
Idarubicin ^f			x	x	x																								
Cytarabine			x	x	x																								
Study Drug (nintedanib/placebo)									x ^g	x	x	x	x	x	x	x	x	x	x	x	x	x	x	x	x	x	x		
AEs ^q																													

a: If these tests are performed within 24 hours of the Cycle 1 Day 1 visit, prior to administration of study drug, they do not need to be repeated on C1 D1, unless otherwise determined by the Principal Investigator.

b: If clinically indicated

c: Complete physical exam and vitals including, weight, blood pressure, pulse, temperature, respiratory frequency, height required at screening only

d: Serum chemistry: AST, ALT, alkaline phosphatase, total bilirubin, BUN, serum creatinine, glucose, calcium, sodium, potassium, magnesium, chloride, bicarbonate, total protein, albumin, LDH, **and uric acid at screening only**

e: Coagulation profile: prothrombin time, activated partial-thromboplastin time, and fibrinogen,

f: Idarubicin may be dose reduced, replace, or omitted according to total dose of anthracycline received by the patient

g: Day 8 Bone Marrow aspirate is optional. If patient consents to D8 optional BMBX, start Nintedanib/placebo on afternoon dose after BMBX and continue until D29 morning dose.

h: Twice weekly

i: Weekly

j: Every other day

k: Performed in patients with complete clearance of blasts in the blood

l: (+/- 1 day)

m: All three tests are required at screening, CXR not required at End of Treatment evaluation; 3d Echocardiogram or biplane Simpson method are acceptable methods for obtaining LVEF

n: differential for CBC done as per hospital standard of care (Required at screening, response evaluation and end of treatment visit)

p: (+/- 7 Days) and decided based on count recovery: Threshold: ANC at 1 and PLT at 50

q: AEs and Concomitant Medications will be assessed on an ongoing basis. AE assessment should begin following C1D1 treatment,

Cycles 2, 3 and 4 (Induction or Consolidation) * To be followed if Cycles, 2, 3 and 4 are Induction and/or consolidation cycles, if patient goes to Maintenance refer to Maintenance Calendar

	Day																													END Of Treatment
	1	2	3	4	5	6	7	8	9	10	11	12	13	14	15	16	17	18	19	20	21	22	23	24	25	26	27	28		
Bidimensional Echography ^j	x																													
Con Meds ^o																														
Physical Exam ^c	x	x ^a			x ^g		x ^{g,b}				x ^g			x ^{g,b}			x ^{g,b}			x ^g			x	x						
ECOG PS																													x	x
CBC with differential ^m	x ⁱ		x ⁱ		x ⁱ			x ⁱ		x ⁱ		x ⁱ		x ⁱ		x ⁱ		x ⁱ		x ⁱ		x ⁱ		x ⁱ		x ⁱ		x ⁱ		x
Serum chemistry ^d											x ^l											x ^l					x	x		
Pregnancy testing ^p	x																													
Coagulation Profile ^e				x ^h						x ^h					x ^h						x ^h									
Idarubicin ^f	x	x	x																											
Cytarabine	x	x	x																											
Study Drug (nintedanib/placebo)							x	x	x	x	x	x	x	x	x	x	x	x	x	x	x	x	x	x	x	x	x	x		
AEs ^o																														x
Correlative Studies (Blood& Bone Marrow)																														x
Bone Marrow Evaluation																														x ^k

a: Induction cycle ONLY

b: Weekly for a Consolidation cycle

c: Complete physical exam and vitals including weight, blood pressure, pulse, temperature, respiratory frequency

d: Serum chemistry: AST, ALT, alkaline phosphatase, total bilirubin, BUN, serum creatinine, glucose, calcium, sodium, potassium, magnesium, chloride, bicarbonate, total protein, albumin, LDH,

e: Coagulation profile: prothrombin time, activated partial-thromboplastin time, and fibrinogen

f: Idarubicin may be dose reduced, replace, or omitted according to total dose of anthracycline received by the patient

g: Twice weekly for an Induction Cycle

h: Weekly; Cycle 2 ONLY

i: Three times weekly

j: Prior to Cycle 2: Any time after Cycle 1 day 14 up to the start of cycle 2; 3d Echocardiogram or biplane Simpson method are acceptable methods for obtaining LVEF

k: Performed in patients with complete clearance of blasts in the blood

l: Every other week

m: differential for CBC will only be done as per hospital standard of care (Required at screening, response evaluation and end of treatment visit)

o: AEs and Concomitant Medications will be assessed on an ongoing basis

p: prior to the start if each new treatment cycle

Maintenance Cycle, End of Treatment & Follow Up

	Maintenance Therapy																				Every 3 months (+/- 7 Days) up to 2 years		
	Monthly (+/- 3 days) for the first 12 months then every 3 months (+/- 7 Days) until disease progression or up to 2 years																						
Month	1	2	3	4	5	6	7	8	9	10	11	12	14	15	16	18	20	21	22	24	End of Treatment	Follow-Up	
Nintedanib ^a	X	X	X	X	X	X	X	X	X	X	X	X	X	X	X	X	X	X	X	X			
Concomitant Medications ⁱ																							
Physical Exam ^b	X	X	X	X	X	X	X	X	X	X	X	X		X		X		X		X	x		
ECOG PS	X	X	X	X	X	X	X	X	X	X	X	X		X		X		X		X	x		
AEs ⁱ																							
CBC with differential ^f	X	X	X	X	X	X	X	X	X	X	X	X	X	X	X								
Serum chemistry ^c	X	X	X	X	X	X		X		X	X		X	X	X		X	x		x			
Pregnancy Testing ^j	X	X	X	X	X	X	X	X	X	X	X	X	X	X	X	X	X	X	X	x ^j	x ^j		
Coagulation Profile ^d	X		X		X																		
EKG, Cardiac Echo ^g																					x		
Bone Marrow Evaluation ^e																					x		
Correlative Studies (Blood & Bone Marrow)																					x		
Hematology, CBC & hemoglobin																					x		
Subsequent anti-cancer therapy, documentation/date of last disease progression/relapse, date of death																						x	

a: Continuous/daily

b: Complete physical exam and vitals including weight, blood pressure, pulse, temperature, respiratory frequency

c: Serum chemistry: AST, ALT, alkaline phosphatase, total bilirubin, BUN, serum creatinine, glucose, calcium, sodium, potassium, chloride, bicarbonate, total protein, albumin,

d: Coagulation profile: prothrombin time, activated partial-thromboplastin time, fibrinogen,

e: Performed in patients with complete clearance of blasts in the blood (+/- 7 Days)

f: differential for CBC will only be done as per hospital standard of care (Required at screening, response evaluation and end of treatment visit)

g: 3d Echocardiogram or biplane Simpson method are acceptable methods for obtaining LVEF

i: AEs and Concomitant Medications will be assessed on an ongoing basis

j: Monthly at the beginning of each Maintenance cycle up until 3 months after last dose of Nintedanib
